7.4 Last Dose of LR769

- Last administration of LR769 (for end of treatment only)
- Efficacy assessment by investigator or designee
- Assessment of concomitant medications
- Postoperative assessment
- Assessment of AEs (including thromboembolic assessments)

7.5 Early Termination Procedures

- Efficacy assessment by investigator or designee
- Assessment of concomitant medications
- Postoperative assessment
- Vital signs
- Clinical safety laboratory tests (hematology, chemistry, urinalysis) by local laboratory; per weight requirement
- Assessment of AEs (including thromboembolic assessments)
- Immunogenicity sample (including storage serum sample for future use)
- Physical Examination (excluding height)

7.6 Follow-Up Visits

7.6.1 48 Hours \pm 4 Hours After the Last Dose of LR769

- Clinical safety laboratory tests (hematology, chemistry, urinalysis), by local laboratory; per weight requirement

- Review of patient diaries and final study drug accountability (including used vials returned by the patient)
- Vital signs
- Efficacy assessment by investigator
- Assessment of concomitant medications
- Postoperative assessment
- Physical examination (excluding height)
- Assessment of AEs (including thromboembolic assessments)
- Immunogenicity sample

7.6.2 28 Days \pm 3 Days After the Last Dose of LR769

- Clinical safety laboratory tests (hematology, chemistry, urinalysis), by local laboratory; per weight requirement
- Assessment of concomitant medications
- Assessment of AEs (including thromboembolic assessments)
- Immunogenicity sample (including storage serum sample for future use)

8 QUALITY CONTROL AND ASSURANCE

This study is sponsored by LFB USA Inc. The Sponsor will delegate specific tasks regarding the conduct of this study to a CRO.

Quality Control Procedures as described in LFB USA's Quality System as well as those of the CRO will be applied. A document describing which procedures will be used for which study activities at each stage of the clinical study will be part of the arrangements between the Sponsor and the CRO. This will ensure patient safety and reliability of the data. Monitoring visits to the study sites will be conducted periodically during the study according a study specific monitoring plan to ensure that all aspects of the protocol are being followed. The study site may be audited by LFB USA's Clinical Quality Assurance auditor (or designee). The study sites will receive written notice in advance of any audit.

9 PLANNED STATISTICAL METHODS

9.1 General Considerations

All data collected in this study will be displayed using summary tables and patient data listings. Continuous variables will be summarized using descriptive statistics, specifically the mean, median, standard deviation, minimum, and maximum. Categorical variables will be summarized by frequencies and percentages.

9.2 Determination of Sample Size

The sample size was determined based on adaptations of international guidelines for coagulation factors in agreement with US and EU authorities.

9.3 Analysis Populations

The Efficacy Population is defined as all patients who receive LR769 treatment, undergo a surgical or invasive procedure, and have at least 1 efficacy assessment.

The Safety Population is defined as all patients who receive at least 1 dose of LR769.

All efficacy analyses will be performed on the Efficacy Population and all safety analyses will be performed on the Safety Population.

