3.3 Study Duration and Dates

The study will continue until at least 12 surgical procedures (including a minimum of 6 major surgeries, of which at least 5 must be procedures other than central venous access device placement) have been performed in at least 6 patients.

The duration of the patient's participation in the study (from signing the Informed Consent form until the last follow-up visit) may vary. In patients undergoing a major procedure the duration of participation will be approximately 6 to 9 weeks (or longer if treatment with LR769 is extended). In patients undergoing a minor procedure the duration of participation will be approximately 5 to 8 weeks (or longer if treatment with LR769 is extended).

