6.14 Replacement of Patients

Patients who are removed from the study will only be replaced if their removal results in the minimum number of surgical or other invasive procedures/patients needed for the study not being met.

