9.5.1 Primary Efficacy Endpoint

The primary efficacy endpoint is the percentage of surgical or other invasive procedures with a “good” or “excellent” response to LR769 treatment as assessed by the investigator at the study center 48 (± 4) hours after the last administration of LR769; this assessment will be based upon the totality of assessments performed on the patient at each timepoint also taking into consideration the surgeon’s intraoperative hemostatic assessment, the number of (interventions for) bleeding episodes, oozing, blood transfusions, and the amount of LR769 used.

A point estimate of this endpoint will be calculated together with a Clopper-Pearson exact 95% confidence interval.

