7.7 Efficacy Endpoints and Analysis

All the Efficacy analyses will be stratified by surgery type and overall. All analyses will then be repeated stratifying by age group (< 12 years and \geq 12 years). Efficacy population will be used for all the analyses described in this section.

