7.7.1 Analysis of Primary Efficacy Endpoint

The primary efficacy endpoint is the percentage of surgical or other invasive procedures with a “good” or “excellent” response to LR769 treatment, as assessed by the investigator at the study center 48 (\pm 4) hours after the last administration of LR769; this assessment will be based upon the totality of assessments performed on the patient at each timepoint, also taking into consideration the surgeon’s intraoperative hemostatic assessment, the number of (interventions for) bleeding episodes, oozing, blood transfusions, and the amount of LR769 used. An additional sensitivity analysis will be performed in which patients whose 48-hour assessment is missing are treated as failures.

The proportion of “good” and “excellent” responses at 48 (\pm 4) hours will be summarized. Clopper-Pearson exact 95% confidence interval for proportion will be calculated for each surgery type and age group and overall. The summaries will include missing assessments in percent calculation, while they will still be discarded when calculating the proportion of successes and the confidence interval (CI). The missing values imputed as per section 7.3 of this SAP will be analyzed as imputed.

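### The Efficacy Population is defined by patient and requires a rating, so a treated patient with no rating falls outside every efficacy analysis, including missing-equals-failure

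*Protocol*

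**What the plan says.** **Who is analysed.** Protocol 9.3, repeated in SAP 6, defines the Efficacy Population on patients: those who receive LR769, "undergo a surgical or invasive procedure, and have at least 1 efficacy assessment". SAP 7.7 adds: "Efficacy population will be used for all the analyses described in this section".

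**Unit of analysis.** SAP 7.1 notes that one patient may enter for several procedures and places efficacy at procedure level. The primary endpoint is a percentage of procedures (Protocol 9.5.1).

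**Missing final ratings.** In the primary analysis, SAP 7.7.1 keeps missing assessments in the percentage summaries, "while they will still be discarded when calculating the proportion of successes and the confidence interval (CI". SAP 7.3 makes one exception: a missing final rating becomes Poor if two conditions on withdrawal and rescue therapy are both met. SAP 7.7.1 then adds a sensitivity analysis in which "patients whose 48-hour assessment is missing are treated as failures".

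**Size and replacement.** Protocol 3.3: "The study will continue until at least 12 surgical procedures", at least 6 of them major, have been performed in at least 6 patients. Protocol 6.14: "Patients who are removed from the study will only be replaced if their removal results in the minimum number" of procedures or patients not being reached.

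**The concern.** Entry to the efficacy set depends on something that happens after treatment, namely that a rating was recorded. The reasons for having none can be related to outcome. The surgeon's rating follows completion of the procedure (Protocol 7.2.3), so an intraoperative death or an abandoned procedure may never receive one. The 24-hour rating is scheduled only while LR769 is ongoing (Protocol 7.3.1). A surgeon's rating may also simply be omitted.

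The SAP change log says the sensitivity analysis was introduced so that a missing primary endpoint counts as failure. It cannot do that for a patient who never enters the set.

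The units also differ. SAP 7.1 moved efficacy to procedure level, but SAP 6 and the sensitivity rule in SAP 7.7.1 are still worded by patient. Two identical unrated procedures could be handled differently because one of the patients happened to be rated at another procedure.

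With a minimum of about 12 procedures and a primary result that is one proportion with its interval, a single omitted failure is visible in the result.

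**Working it through.** **Step 1. Trace a treated procedure with no final rating through the plan.** The two-condition imputation in SAP 7.3 is set aside here. SAP 7.3 does not say that an imputed rating satisfies the entry requirement, and I read it as not doing so.

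| Situation | In Efficacy Population? | Primary proportion | Missing-equals-failure |
|---|---|---|---|
| Some other rating exists for this procedure | Yes | Dropped | Failure |
| No rating for this procedure; patient rated at another | Patient yes; procedure not settled | Dropped | Not settled |
| Patient has no rating at any procedure | No | Absent | Absent |

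The sensitivity analysis works in the first row, is undefined in the second and fails in the third.

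**Step 2. The plan's own figure.** The minimum of 12 procedures cannot be reproduced by calculation. Protocol 9.2 gives only this basis: "The sample size was determined based on adaptations of international guidelines for coagulation factors in agreement with US and EU authorities". No target rate, precision or expected missing rate is stated, and no stated figure is wrong.

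**Step 3. Size of the effect.** Protocol 9.5.1 fixes the method: "A point estimate of this endpoint will be calculated together with a Clopper-Pearson exact 95% confidence interval". For x successes in n:

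- lower limit = the 0.025 quantile of Beta(x, n − x + 1); when x = n this is 0.025^(1/n)
- upper limit = the 0.975 quantile of Beta(x + 1, n − x); when x = n it is 1

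Check: 0.025^(1/12) = 0.7354, so 12/12 has a lower limit of 73.5%.

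The number k of treated, wholly unrated failures is an assumption, as is success at every other procedure.

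| Case | Sensitivity analysis as planned | All treated procedures, unrated = failure |
|---|---|---|
| 12 treated, k = 1 | 11/11 = 100% (71.5 to 100) | 11/12 = 91.7% (61.5 to 99.8) |
| 12 treated, k = 2 | 10/10 = 100% (69.2 to 100) | 10/12 = 83.3% (51.6 to 97.9) |
| Replaced up to 12 rated, k = 1 | 12/12 = 100% (73.5 to 100) | 12/13 = 92.3% (64.0 to 99.8) |
| Replaced up to 12 rated, k = 2 | 12/12 = 100% (73.5 to 100) | 12/14 = 85.7% (57.2 to 98.2) |
| Major stratum, replaced up to 6, k = 1 | 6/6 = 100% (54.1 to 100) | 6/7 = 85.7% (42.1 to 99.6) |

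For k = 1 overall, the rate differs by 100 − 91.7 = 8.3 points, or 100 − 92.3 = 7.7 points with replacement. The lower limit differs by 71.5 − 61.5 = 10.0 points, or 73.5 − 64.0 = 9.5 points.

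**Step 4. Replacement.** Protocol 3.3 counts procedures that have been performed. Protocol 6.14 supposes that removing a patient can take the study below its minimum. Neither says whether a treated, performed procedure still counts toward the 12 after its patient is removed. The replacement rows above apply only if it does not.

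**The case against.** The strongest reply is that very few procedures can leave by this route. Any single rating admits the patient. The surgeon rates immediately after the procedure (Protocol 7.2.3), and there are further ratings at last dose (7.4) and at early termination (7.5). Withdrawn patients are asked to attend the 48-hour visit unless consent is withdrawn (6.13). Unexpected transfer to intensive care is itself a criterion for Poor (6.8), so that kind of bad outcome is meant to be rated. The omission would not be hidden either: SAP 7.4 reports the numbers in the Safety and Efficacy Populations, withdrawals with reasons, and deaths. Efficacy is descriptive (Protocol 9.5), so no decision rule would change. All of this stands, and it is why the point is a modest one.

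A reader might infer three stronger things, none of which the documents support:

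- **Procedures that go badly drop out and are replaced.** Replacement under 6.14 applies only when the minimum is not met, and it deletes no rated patient from the analysis.
- **Missing-equals-failure can never recover an unrated procedure.** This is certain only when the patient has no rating at any procedure. Otherwise the procedure may be kept and counted as a failure.
- **This is the main way failures are lost.** The wider loss is the discarding of missing final ratings in the primary analysis, and the sensitivity analysis does recover those for patients in the set.

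The reply leaves two things unanswered. The patient with no rating is in neither analysis, and the patient-based set is not reconciled with a procedure-based endpoint. The disposition table would show that someone is missing, but no planned estimate would include that patient.

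**Conclusion.** The point holds as a narrow gap in definitions. Entry to the efficacy set depends on a post-treatment rating. The analysis meant to count missing results as failures is confined to that set, and the set's unit does not match the endpoint's. Protocol 6.14 is also silent on whether a treated, performed procedure still counts after removal.

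If one such failure occurred and every other procedure succeeded, the success rate in the sensitivity analysis would be overstated by about 8 points and its lower confidence limit by about 10. These sizes rest on an assumed number of lost failures; the documents give no expected rate, and it may well be zero. If every treated procedure receives at least one rating and is kept, no result changes.

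**What to change.** - **Protocol 9.3 and SAP 6:** define the efficacy set by procedure, as every procedure started after at least one LR769 dose, with or without a rating.
- **SAP 7.7.1:** run missing-equals-failure on that set, worded in procedures instead of patients. Report the number of treated but unrated procedures, with reasons.
- **Protocol 6.14:** state that a treated, started procedure stays in the denominator after its patient is removed, and that any replacement is additional.

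The cost is wording in both documents; no new data are needed, and SAP 7.1 allows updates before database lock. Because the primary proportion discards missing final ratings, apart from those imputed under SAP 7.3, the change falls mainly on the sensitivity analysis. The downside is that this supportive success rate may be slightly lower.

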9.4 Demographics and Baseline Characteristics

Demographic and baseline characteristics for all patients will be summarized using descriptive statistics for continuous variables and frequencies and percentages for categorical variables.

9.5 Efficacy Endpoints

Efficacy results will be reported as descriptive statistics. Surgeries will be examined overall as well as by major procedures and minor procedures separately.

9.5.1 Primary Efficacy Endpoint

The primary efficacy endpoint is the percentage of surgical or other invasive procedures with a “good” or “excellent” response to LR769 treatment as assessed by the investigator at the study center 48 (± 4) hours after the last administration of LR769; this assessment will be based upon the totality of assessments performed on the patient at each timepoint also taking into consideration the surgeon’s intraoperative hemostatic assessment, the number of (interventions for) bleeding episodes, oozing, blood transfusions, and the amount of LR769 used.

A point estimate of this endpoint will be calculated together with a Clopper-Pearson exact 95% confidence interval.

9.5.2 Secondary Efficacy Endpoints

The secondary efficacy endpoints are:

- Percentages of success as defined as the combination of “good” and “excellent” responses by the investigator or designee for all efficacy timepoints other than the primary
- Percentages of “poor,” “moderate,” “good,” and “excellent” response by the investigator or designee for all efficacy timepoints
- Percentages of success as defined as the combination of “good” and “excellent” responses by the surgeon/practitioner
- Percentages of “poor,” “moderate,” “good,” and “excellent” response by the surgeon/practitioner for the intraoperative period
- Intraoperative blood loss determined by the surgeon/practitioner as compared to the surgeon/practitioner’s maximum predicted blood loss
- Number of events requiring transfusion between start of procedure and 48 (\pm 4) hours after last administration of LR769
- Changes in hemoglobin between start of procedure and 48 (\pm 4) hours after last administration of LR769
- Amount of LR769 used. Total, and separated by use in hospital, at home, or for specific reasons (eg, physical therapy, or other reasons like drain or suture removal)
- Number and type of bleeding episodes at the surgical site between start of procedure and 48 (\pm 4) hours after last administration of LR769
- Number of surgical interventions/re-explorations for bleeding episodes between start of procedure and 48 (\pm 4) hours after last administration of LR769

Point estimates will be computed together with 95% confidence intervals for the proportion of successes, mean difference between intraoperative blood loss and surgeon/practitioner’s maximum predicted blood loss, proportion of events requiring transfusion, mean hemoglobin level at each timepoint, mean amount of LR769 used, and mean number of surgical interventions/re-explorations for bleeding episodes. Clopper-Pearson exact confidence intervals will be used for dichotomous endpoints; confidence intervals for continuous variables will be based on the normal approximation.

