5.2.2 Treatment for Major Surgical Procedures

The initial dose of LR769 (200 µg/kg) will be followed by repeated administration of 75 µg/kg of LR769 every 2 hours (±5 minutes) for the first 48 hours after completion of the procedure. The minimum duration of LR769 treatment for major procedures will be 5 days, according to the frequency listed in the [table below](#).

Table 1. Dose(s) and Dosing Schedule(s) for Major Surgical Procedures

Day	Dose	Recommended Frequency
Day 0 (within 2 minutes of surgical incision or invasive procedure)	200 µg/kg	Initial dose
Day 0 (post first dose) – 48 hours	75 µg/kg	Every 2 hours (±5 minutes)
Days 3- 4	75 µg/kg	Intervals of up to every 4 hours but not more frequently than every 2 hours
Days 5-6	75 µg/kg	Intervals of up to every 6 hours but not more frequently than every 2 hours
Days 7-10	75 µg/kg	Intervals of up to every 8 hours but not more frequently than every 2 hours
Day 11 to Last Administration of LR769	75 µg/kg	Intervals of up to every 12 hours but not more frequently than every 2 hours

NOTE: If clinically indicated because of oozing or similar findings suggesting the need for more frequent LR769 infusions, the treatment interval may be shortened in consecutive doses within the guidelines stated in Table 1.

If the patient requires further treatment with LR769 after hospital discharge, the patient will administer LR769 at home according to the investigator’s judgment and the dosing guidelines specified in Table 1. The patient will be provided with LR769 and directions for its storage, reconstitution and administration along with a patient diary in which to record LR769 administration.

If physical therapy is planned, an IV bolus dose of 75 µg/kg of LR769 administered within ≤2 minutes is recommended each time before the therapy begins. Similarly, before drain or suture removal, an IV bolus dose of 75 µg/kg of LR769 administered within ≤2 minutes is recommended.

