5.2.3 Treatment for Minor Surgical or Other Invasive Procedures

The initial dose of LR769 (75 µg/kg) will be followed by repeated administration of 75 µg/kg of LR769 every 2 hours (±5 minutes) for the first 48 hours. The minimum duration

of LR769 infusion for minor procedures will be 2 days, according to the frequency listed in the table below.

Table 2. Dose(s) and Dosing Schedule(s) for Minor Surgical or Other Invasive Procedures

Day	Dose	Recommended Frequency
Day 0 (within 2 minutes of surgical incision or invasive procedure)	75 µg/kg	Initial dose
Day 0 (post first dose) – 48 hours	75 µg/kg	Every 2 hours (±5 minutes) initially. Interval may be increased upon the investigator's judgment
Day 3 to Last Administration of LR769	75 µg/kg	Intervals of up to every 24 hours but not more frequently than every 2 hours

*For less invasive procedures, such as PICC or Port-a-Cath placement and for procedures such as dental extractions, the patient may be treated for ≤48 hours if the investigator or designee determines this shorter duration of treatment is sufficient to achieve hemostasis.

NOTE: If clinically indicated because of oozing or similar findings suggesting the need for more frequent LR769 infusions, the treatment interval may be shortened in consecutive doses within the guidelines stated in Table 2.

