6.11 Concomitant Medication Assessments

All concomitant medications (including any blood or blood products) and/or concomitant procedures administered or performed during the study will be recorded in the source record and subsequently captured in the eCRF (including date, time, type of medication or product, and dose or amount).

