6.13 Removal of Patients from the Trial or Treatment

The investigator may withdraw a patient from the study for any of the following reasons:

- The investigator believes it is in the best interest of the patient to discontinue the study
- The Sponsor or investigator terminates the study
- The patient withdraws consent or requests to be discontinued from the study
- The patient is non-compliant

In case of early withdrawal of the patient, he will be asked to perform the 48 (\pm 4) hour visit assessment after last administration of LR769, unless he has withdrawn Informed Consent.

The investigator may discontinue a patient from LR769 treatment for any of the following reasons:

- AE or SAE possibly related to LR769 treatment
- A clinically significant change in the patient's condition that does not allow safe administration of LR769
- Per judgment of the investigator, if an adequate hemostatic response is not achieved with LR769, and the bleeding requires continued treatment, the treating physician should stop treatment with LR769 and treat the patient with a rescue therapy, such as another bypassing agent (e.g., FEIBA® or NovoSeven®) and/or other effective hemostatic treatment. The patient remains eligible for treatment with LR769 for a new surgical procedure taking into account the pharmacodynamic half-life of the rescue therapy given.

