7.7.2 Analysis of Secondary Efficacy Endpoints

The following endpoints are considered secondary for this study:

- Percentages of success as defined as the combination of “good” and “excellent” responses by the investigator or designee for all efficacy timepoints other than the primary
- Percentages of “poor,” “moderate,” “good,” and “excellent” response by the investigator or designee for all efficacy timepoints
- Percentages of success as defined as the combination of “good” and “excellent” responses by the surgeon/practitioner for the intraoperative period
- Percentages of “poor,” “moderate,” “good,” and “excellent” response by the surgeon/practitioner for the intraoperative period
- Intraoperative blood loss determined by the surgeon/practitioner as compared to the surgeon/practitioner’s maximum predicted blood loss
- Number of events requiring transfusion between start of procedure and 48 (±4) hours after last administration of LR769
- Changes in hemoglobin between start of procedure and 48 (±4) hours after last administration of LR769
- Amount of LR769 used. Total, and separated by use in hospital, at home, or for specific reasons (eg, physical therapy, or other reasons like drain or suture removal)
- Number and type of bleeding episodes at the surgical site between start of procedure and 48 (±4) hours after last administration of LR769
- Number of surgical interventions/re-explorations for bleeding episodes between start of procedure and 48 (±4) hours after last administration of LR769

The first four secondary endpoints will be analyzed similarly to the primary endpoint: numbers and percentages of successes will be summarized at each timepoint, together with their Clopper-Pearson exact confidence limits.

Difference between the expected and actual blood loss will be calculated for each surgery in the study and then summarized together with 95% confidence limits. Number of events requiring transfusion, Number of bleeding episodes (by type) at the surgical site between start of procedure and 48 (±4) hours, and Number of surgical interventions/re-explorations for bleeding episodes between start of procedure and 48 (±4) hours after last administration of LR769 will be analyzed similarly.

Hemoglobin levels will be summarized at baseline and at 48 (±4) hours after last administration of LR769. Changes from baseline will also be summarized for 48 (±4) hours timepoint. 95% confidence limits for the changes will be displayed.

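### Transfusions, surgical-site bleeds and re-explorations are counted only to 48 h after the last LR769 dose, so an early failure switched to rescue is counted over a shorter window

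*Protocol*

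**What the plan says.** Protocol 9.5.2 lists three event counts with one common window: "Number of events requiring transfusion between start of procedure and 48" (±4) hours after the last LR769 administration, "Number and type of bleeding episodes at the surgical site between start of procedure and 48" (±4) hours after it, and the matching count of re-explorations. SAP sections 5 and 7.7.2 repeat them, for example "Number of surgical interventions/re-explorations for bleeding episodes between start of procedure and 48" (±4) hours after the last administration.

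SAP 7.7.2 summarises the counts per surgery with 95% confidence limits. It gives no rate per day, no window common to all procedures and no rule for events after rescue. Its analysis sentence for bleeding episodes gives 48 (±4) hours without repeating the last-dose anchor.

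Four other provisions matter:

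- **Failure.** Protocol 6.13 says that when hemostasis is inadequate and bleeding needs continued treatment, "the treating physician should stop treatment with LR769 and treat the patient with a rescue therapy, such as another bypassing agent". The same section lists stopping LR769 separately from leaving the study.
- **Course length.** For major procedures, "The minimum duration of LR769 treatment for major procedures will be 5 days" (protocol 5.2.2). For minor ones, the minimum duration "of LR769 infusion for minor procedures will be 2 days" (protocol 5.2.3), with 48 h or less allowed after less invasive procedures.
- **Data collected.** Protocol 6.11: "All concomitant medications (including any blood or blood products) and/or concomitant procedures administered or performed during the study will be recorded". Protocol 5.5 has blood products recorded, with date and time, to the end of follow-up. Adverse events are analysed to 28 (±3) days after the last dose (protocol 9.6).
- **Site checks.** The synopsis runs postoperative site assessments in hospitalized patients to 48 (±4) h after the last dose. The 28-day visit (protocol 7.6.2) has none.

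**The concern.** An event count can be compared between procedures only if each is observed for a similar time, or if the time is allowed for. Here the observation time depends on the outcome. If LR769 fails early, the failure fixes the date of the last dose and counting ends about two days later, even if the same bleed still needs transfusion or re-exploration under another agent. A major procedure that completes the minimum course is counted for a week.

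This is a single-arm, descriptive study whose primary endpoint is an investigator's rating. These three counts are among its more objective supporting evidence. The stated minimum is 6 major procedures, so a single early failure carries weight in the major-procedure mean.

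**Working it through.** The plan states no figure for window length, so there is none to reproduce. The lengths follow from its definitions.

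**Inputs from the documents:** 48 (±4) h after the last dose (protocol 9.5.2); minimum course 5 days for major and 2 days for minor procedures (protocol 5.2.2, 5.2.3); at least 6 major procedures (SAP 4).

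**Assumed:** the times at which LR769 is stopped for failure, the event rates in the illustration, and that minimum durations run from the start of the procedure.

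**Formula:** window = time from start of procedure to last LR769 dose + 48 h.

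*Completed minimum course*

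- Major: 5 × 24 + 48 = 168 h (164 to 172 h with the tolerance).
- Minor: 2 × 24 + 48 = 96 h (92 to 100 h).

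*LR769 stopped for failure*

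| Last dose at (assumed) | Window | Share of 168 h (major) | Share of 96 h (minor) |
|---|---|---|---|
| 6 h | 54 h | 32% | 56% |
| 12 h | 60 h | 36% | 62.5% |
| 24 h | 72 h | 43% | 75% |
| 48 h | 96 h | 57% | 100% |
| 120 h | 168 h | 100% | longer than the minimum |

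The shortfall is confined to stops before the minimum course is complete. From 120 h (major) or 48 h (minor) onward, a failure loses nothing against a minimum completer.

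The window also stretches the other way. A procedure kept on LR769 to day 10 is counted for 10 + 2 = 12 days (288 h), which is 288/168 = 171% of the minimum window.

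*What the lost time could mean in events.* The documents give no event rates, so this only illustrates sensitivity. Take 6 major procedures: five minimum completers at 0.05 events/day and one failure stopped at 24 h with a constant rate r. The failure is counted for 3 days instead of 7.

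- Mean as defined = (5 × 0.05 × 7 + 3r)/6
- Mean over a fixed 7 days = (5 × 0.05 × 7 + 7r)/6

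| r (events/day, assumed) | As defined | Fixed 7 days | Under-count |
|---|---|---|---|
| 0.2 | 0.39 | 0.53 | 25% |
| 0.5 | 0.54 | 0.88 | 38% |
| 1.0 | 0.79 | 1.46 | 46% |

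Without a rate model, each uncounted event in one of 6 major procedures lowers the mean by 1/6 = 0.17, and two lower it by 2/6 = 0.33. If all the events fall before the stop or in the 48 h after it, nothing is lost.

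*Can the missing period be recovered?* Transfusions and re-operations: yes, from the records required by protocol 5.5 and 6.11. Surgical-site bleeds: only in part. After a stop at 24 h, no scheduled site assessment falls between 72 h and 168 h, so a bleed in that gap would have to come from adverse-event or procedure records.

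**The case against.** The strongest reply is that a reader might infer more than the documents support, in four ways.

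- **That the mean counts are biased in favour of LR769 overall.** This is not shown. Treatment lasts as long as hemostasis requires, so a patient who oozes but stays on LR769 is counted longer. Some minor courses are short because hemostasis came quickly. Both push against the early-failure effect.
- **That a failed procedure shows only 36 to 43% of its events.** Those are shares of time. Equating them with events needs a constant and equal rate. The events that prompt rescue come before the stop and are counted, as are those in the next 48 h, including under rescue.
- **That later events disappear.** They leave these three summaries only. SAP 7.7.2 plans listings of transfusions, interventions and bleeding episodes with no stated cut-off, and adverse events are analysed to 28 days. A transfusion first given after the treatment period would, however, also miss the concomitant-medication table, given the definition in SAP 7.9.2.
- **That failure goes unseen.** Uncontrolled bleeding that requires rescue meets the definition of a poor response (protocol 6.8), so the primary endpoint largely registers it.

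It is also true that the endpoints are secondary and descriptive, with no test or success criterion resting on them, and that events under rescue are partly outcomes of another product.

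All of this limits the size of the point. None of it makes the three counts comparable between procedures, and late events may continue the bleed that LR769 did not control. Showing events before and after the switch answers the attribution question; cutting them off does not.

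**Conclusion.** The point holds in a limited form. When LR769 is stopped early for inadequate hemostasis, the failure closes the counting window for all three endpoints. In a major procedure stopped at 12 to 24 h, the window is 60 to 72 h against at least 168 h. In minor procedures the gap is smaller, and after the minimum course it vanishes relative to a minimum completer. Events beyond about 48 h after an early stop are omitted from these summaries, so the counts can understate what happened in early failures and cannot be compared directly between procedures.

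The window arithmetic rests on the protocol's minimum durations counted from the start of the procedure and on assumed stop times. The 25 to 46% under-count also rests on assumed event rates and is not a prediction. The direction and size of any net bias over all procedures are not established.

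**What to change.** Keep the stated endpoints. Add to SAP 7.7.2 a supplementary count over one fixed window from the start of the procedure, whatever hemostatic agent is in use: for example 7 days for major and 4 days for minor procedures, which is the minimum course plus 48 h. Show events before and after any switch to rescue separately.

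- **Transfusions and re-explorations:** apply the fixed window directly; the records already exist.
- **Surgical-site bleeds:** report the same window from adverse-event and procedure records, with a footnote that scheduled site assessments end 48 h after the last LR769 dose and later bleeds may be under-recorded.
- **Wording:** state the last-dose anchor in the SAP 7.7.2 analysis sentence for bleeding episodes, to match the endpoint definition.

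Running the count to 48 h after the last rescue dose would not solve the problem. Window length would still depend on outcome, now through the duration of rescue, and rescue would need a definition that separates it from the antifibrinolytics permitted alongside LR769 (protocol 5.6.1).

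The cost is one extra table and a few lines of SAP text, with no new visits and no change in treatment. The supplementary counts may look slightly less favourable and will include events under rescue.
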